### 15.4 Analysis of Secondary Endpoints

Using two separate mixed effects logistic regressions and marginal plots, we will estimate, graph, and compare probabilities of a negative urine test and viral suppression over time between those with methamphetamine use disorder in the contingency management (MA+/HIV+) and non-substance-using control (MA-/HIV+) conditions.

### 15.5 Interim Analysis

Interim analysis will take place on the primary and secondary endpoints after all participants complete of Week 4 of the study using the modeling approaches described above. Additionally, an interim analysis for safety will be conducted when 25% of participants complete Week 4.

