CONTROL GROUP	
Those in the non-substance-using control condition (MA-/HIV+) will only not receive an intervention. They will only attend four appointments total after their screening to provide blood draws, urine samples, and complete their behavioral surveys.

DURATION OF SUBJECT PARTICIPATION AND DURATION OF STUDY	
Each subject will be on study for up to 17 weeks
 
Screening period: 1-4 weeks
 
Baseline assessment: 1 week
 
Treatment: 8 weeks
 
Follow-up: 4 weeks after end of treatment
 
The total duration of the study is expected to be 4 years. 1 year of rolling subject recruitment, 1 year for final subject follow-up, 1 year of biospecimen processing, and 1 year of analysis.

CONCOMITANT MEDICATIONS	NONE
EFFICACY EVALUATIONS	
PRIMARY ENDPOINT	
 
• A gene expression (mRNA) pattern called the conserved transcriptional response to adversity (CTRA) will be measured using transcriptome profiling of leukocytes.
 

SECONDARY ENDPOINTS	
 
• Negative urine tests for methamphetamine
 
• HIV viral load from plasma
 

OTHER EVALUATIONS	
 
• Plasma concentration of methamphetamine
 
• Short Inventory of Problems Revised (SIP-R)
 
• Sociodemographics – age, race, education level, sexual orientation, housing status, body mass index (BMI), smoking history, and heavy alcohol use history
 

SAFETY EVALUATIONS	
 
• MA use frequency based on urine tests
 
• HIV viral load
 
• Incidence of adverse events
 

PLANNED INTERIM ANALYSES	This will be an NIH-funded study through the K01 mechanism. We have just received requested for Just In Time. When approximately

	50% of patients have completed the study through Week 4, an interim analysis for safety will be conducted when 25% of participants complete Week 4. Serious adverse events will be monitored by the investigators on an ongoing basis throughout the study.
STATISTICS	

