### 4 STUDY DESIGN

#### 4.1 Study Overview

The proposed study will be a two-arm clinical trial design of 55 MSM living with HIV, of whom 35 HIV-positive MSM with MUD (MA+/HIV+) will receive contingency management for MA reduction, and 20 HIV-positive, non-substance-using MSM (MA-/HIV+) will participate as a control. There is extensive evidence that CM has greater efficacy than a non-contingent condition in the treatment of MUD (41-44, 46-49, 88), so it may raise ethical concerns to withhold CM from people with MUD who are willing to receive treatment. For this reason, this study uses a control of non-substance using HIV-positive (MA-/HIV+) MSM rather than a non-contingent yoked control of HIV-positive MSM with MUD (89). The use of a non-substance-using HIV-positive control will provide a baseline level of CTRA among HIV-positive MSM who do not have MUD or use other substances, which can be compared against CTRA levels in those with MUD. Screening data will be reviewed to determine subject eligibility. Subjects who meet all inclusion criteria and none of the exclusion criteria will be entered into the study. The following treatment regimens will be used:

- Contingency management twice weekly for 8 weeks, with post-treatment follow-up at Week 12.

- Non-substance-using control will not receive a treatment, but will be evaluated at Baseline, Weeks 4, 8, and 12.

The total duration of subject participation will be 14 weeks. The total duration of the study is expected to be 4 years: 1 year of rolling subject recruitment, 1 year for final subject follow-up, 1 year of biospecimen processing, and 1 year of analysis.

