## 9.3 Research Laboratory Measurements

### 9.3.1 Leukocyte Transcriptome Profiling – Conserved transcriptional response to adversity (CTRA)

Biomarkers of immune functioning will be measured based on leukocyte transcriptome profiling from PBMCs. To quantify abundance of genes expressed, my collaborators and I will conduct

supervised transcriptional profiling of participants from PBMCs using methods previously established and validated procedures of CTRA profiling (11, 90). Blood draws will be obtained via venipuncture at 4 visits: Baseline, Visit 4.2 (Week 4), Visit 8.2 (Week 8), and Visit 12.0 (Week 12). PBMCs will be extracted at an external laboratory and stored at -70°C. The PBMC samples will be transferred to our clinical collaborators, [name] and the UCLA Social Genomics Core Laboratory, where mRNA will be extracted using Qiagen RNeasy standard methods, converted to cDNA libraries using the mRNA-targeted Lexogen QuantSeq 3’ FWD enzyme system, and sequenced on an Illumina HiSeq 4000 instrument in the UCLA Neuroscience Genomics Core Laboratory, all following the manufacturers’ standard protocols. Sequencing will target >10 million 65 nt forward strand reads per sample, which will be mapped to the human transcriptome using the STAR aligner, quantified as gene transcripts per million mapped reads, log2-transformed for analysis, and further normalized if needed to standardize the expression of 11 pre-established housekeeping gene transcripts (91).

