### 15.3 Analysis of Primary Endpoint

Using mixed effects linear regression and marginal plots, we will estimate, graph, and compare trajectories of CTRA gene expression between those with methamphetamine use disorder in the contingency management (MA+/HIV+) and non-substance-using control (MA-/HIV+) conditions.

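### Section 15.5 plans an endpoint interim with no purpose, alpha or decision rule; the synopsis omits it, and for CTRA it comes ahead of the planned sample processing

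*Combined protocol and SAP*

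**What the plan says.** Section 15.5 of the combined protocol and SAP contains two interim looks. The first covers efficacy: "Interim analysis will take place on the primary and secondary endpoints after all participants complete of Week 4 of the study", to be done "using the modeling approaches described above". The models above it are those of 15.3 and 15.4. Section 15.3 says of the primary endpoint that "we will estimate, graph, and compare trajectories of CTRA gene expression" by mixed model, and 15.4 does the equivalent for negative urine tests and viral suppression. The second look is for safety, at 25% of participants through Week 4.

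The planned-interim row of the synopsis has only the safety look, in a sentence with two triggers: "50% of patients have completed the study through Week 4, an interim analysis for safety will be conducted when 25% of participants complete Week 4".

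On timing, section 4.1 (and the synopsis) expects four years in this order: "1 year of rolling subject recruitment, 1 year for final subject follow-up, 1 year of biospecimen processing, and 1 year of analysis".

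Three further points bear on this:
- The opening of section 15 requires the detailed SAP only before the final data are analysed, not before an interim.
- Section 9.3.1 takes blood for CTRA at Baseline and Weeks 4, 8 and 12 and stores PBMCs at -70°C. It describes housekeeping-gene normalisation if needed and no sequencing batch scheme.
- No significance level, boundary or stopping rule for efficacy appears anywhere.

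**The concern.** A reader cannot tell from the documents whether an endpoint look is planned at all, since the synopsis and 15.5 disagree. If it is planned, nothing says what it is for or what may follow from it. Three things are at stake.

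- **Error control.** An unadjusted second look raises the type I error if a result from either look may be claimed.
- **Pre-specification.** The SAP may be written after the interim, so CTRA scoring, covariates and model form could be settled once outcome data have been seen. This risk exists even if nothing is claimed at the interim.
- **Assay batches.** CTRA comes from sequencing stored cells. Sequencing part of the samples early leaves a remainder made up only of late visits, so batch becomes linked to visit. Time is a term in the CTRA models, and such a link is hard to undo after sequencing.

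**Working it through.** **The plan's own totals (15.7).** 55 participants × 4 draws = 220 person-observations; 220 × 0.80 = 176. Both reproduce. The interim has no stated figure of its own to check.

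**Information at the look.** Two cases:
- Baseline and Week 4 only: 55 × 2 = 110, so t = 110/220 = 0.50.
- All accrued data, assuming uniform enrolment over the 52-week recruitment year, no dropout, and the look taken when the last participant reaches Week 4. The share past Week 8 is (52 − 4)/52 = 0.923 and the share past Week 12 is (52 − 8)/52 = 0.846. Then t = (1 + 1 + 0.923 + 0.846)/4 = 0.942, or about 207 of 220 observations.

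**Two-look error for one endpoint.** Assume two-sided 0.05 at each look and that significance at either look counts. With Z₁ and Z₂ bivariate normal and correlation √t, the error is 1 − P(|Z₁| ≤ 1.96 and |Z₂| ≤ 1.96).

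| Data at interim | t | √t | Error | Equal level per look restoring 0.05 |
|---|---|---|---|---|
| All accrued | 0.942 | 0.971 | 0.061 | 0.041 |
| Baseline and Week 4 | 0.50 | 0.707 | 0.083 | 0.029 |

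These fractions count observations. A time slope from the first two draws alone carries less information (t about 0.13 with draws at weeks 0, 5, 9 and 13), and the same formula gives 0.094.

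For three endpoints treated as independent, the final look alone gives 1 − 0.95³ = 0.143. Both looks give 1 − (1 − 0.061)³ to 1 − (1 − 0.083)³, about 0.173 to 0.229. Much of that total therefore comes from having several endpoints rather than from the interim.

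**Samples left for a later batch.** At the look, every retained participant has given Baseline and Week 4 blood, so whatever remains is late-visit:
- Week 8 outstanding: 55 × 4/52 = 4.2
- Week 12 outstanding: 55 × 8/52 = 8.5
- Total: about 13 of 220. About 110 − 13 = 97 Week 8 and Week 12 samples would already be in hand.

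If the laboratory ran only Baseline and Week 4 samples first, the later batch would hold 110 samples and batch would coincide fully with early versus late visits.

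**Effect of a batch shift b.** Both arms give PBMCs at the same visits. In the full split, the early-to-late change is δ₁ + b in the contingency management arm and δ₀ + b in the controls. The difference is δ₁ − δ₀, so an additive shift common to both arms drops out of the between-group comparison in 15.3. It stays in any overall time effect (δ + b). In the partial split, the shift falls on late visits of the last enrollees, and cancellation also needs the arms to be similarly represented among them.

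**The case against.** The strongest reply is that the documents show no harm as such. A reader might infer that type I error is inflated outright. That does not follow: no alpha is stated, 15.3 and 15.4 speak of estimating, graphing and comparing, and the explicit testing language is in 15.6, which comes after 15.5. All participants have passed Week 4 by then, so enrolment is complete. A look that supports no claim and changes nothing leaves the final test at its nominal level. This stands, and the error figures are conditional for that reason.

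A reader might also infer that the timeline forbids the interim. It does not. It is an expected sequence of years, and 15.5 sets an earliest time rather than a date. Urine results do not depend on sequencing, viral load is listed as a clinical laboratory measure, and section 16.4 foresees interim reports. What stands is narrower: a CTRA look soon after the last Week 4 visit does not fit the planned order.

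A third tempting reading is that batch is fully confounded with visit. No section describes batches, and that outcome needs about 97 late samples already in hand to be left out. The remainder of about 13 is nonetheless all late-visit.

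Finally, this is a non-randomised pilot, and the later SAP may modify the analyses. But that SAP need not precede the interim, so it does not close the gap.

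**Conclusion.** The concern holds in conditional form. Section 15.5 plans a look at the primary and secondary endpoints that the synopsis does not list, with no purpose, alpha or decision rule, and for CTRA it comes ahead of the planned processing year.

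If both looks were tested at two-sided 0.05 and either could support a claim, one endpoint's error would be about 6.1% (all accrued data) to 8.3% (Baseline and Week 4 only). The 0.05 level and uniform 52-week accrual are assumptions, not figures from the documents. If CTRA were sequenced early, between about 13 and 110 of 220 samples, all from Week 8 or Week 12, would fall in a later batch. A shift common to both arms would largely cancel in the between-group trajectory comparison but not in overall time effects.

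The documents do not support saying that error is inflated regardless of use, that the timeline rules the interim out, or that batch is necessarily aliased with visit. A change is still warranted, because the second look is uncontrolled, the possible bias is avoidable, and the remedy is nearly free.

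**What to change.** - Remove the endpoint interim from 15.5. Alternatively, restrict it to estimates without p-values, state that it supports no claim, and keep the final test at its full level.
- Require the SAP to be final before any look at the endpoints, not only before the final analysis.
- State in 9.3.1 that CTRA sequencing starts after the last Week 12 sample, with each participant's four samples in one batch and the arms balanced across batches. Frozen storage and the existing timeline already allow this.
- Reconcile 15.5 with the synopsis on which interim looks exist, and resolve the 50% and 25% triggers in the synopsis sentence on the safety look.

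The cost is wording in the protocol and SAP, with no change to sample size or visits. The sponsor gives up an early look to which the documents attach no decision.

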### 15.6 Multivariate Analysis for Associations Between Endpoints

Associations between MA use, CTRA gene expression, and viral suppression. All models in Aim 1 will adjust for age, race, education, employment, housing, and mRNA encoding markers of major leukocyte subsets (e.g., CD4). We will also assess for confounding by COVID-19 infection detected by immunoassay, liver function, and type of ART prescription. MA use and CTRA. Using a linear mixed effects regression, we will test whether a negative MA urine test is associated with reductions in CTRA contrast scores across four time points—Visits B, 4.2, 8.2, and 12.0. We will use a time (days) by MA urine result interaction term to estimate difference in change in CTRA as

a function of MA test result. CTRA and viral load. Using a mixed effects logistic regression, we will test whether CTRA gene expression is associated with viral suppression (<200c/mL) across three time points—Visits B, 4.2, 8.2, and 12.0. We will include a time (days) by CTRA gene expression interaction term to test this association longitudinally. We will also test whether CTRA and viral load are reciprocally associated using dynamic panel data modeling with maximum likelihood (102-104). This approach will allow us to simultaneously test whether CTRA is associated with viral load at subsequent observations, and account for whether CTRA is affected by prior values of viral load (102-104).

**Associations between psychosocial indicators of substance use severity and CTRA.** Using a linear mixed effects regression, I will test whether the seven domains of the Addiction Severity Index (ASI) is associated with reductions in CTRA contrast scores across four time points—Visits B, 4.2, 8.2, and 12.0. I will use a time (days) by ASI domain score interaction term to estimate change in CTRA as a function of changes in ASI scoring. We will control for age, race, education, and mRNA markers of major leukocyte subsets.

**Indirect associations between MA use, CTRA, and viral suppression.** I will use propensity scores to test the degree to which CTRA mediates the association between MA use and viral suppression (105, 106). The general theory is that we would compute propensity score for CTRA—the probability of having a particular CTRA level—to compare participants who used MA with those who would have had the same value of the CTRA had they used MA.

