### **5.4 Other Evaluations**

We will assess psychosocial problems with substance use using the Short Inventory of Problems-Revised (SIP-R). Sociodemographics – age, race, education level, sexual orientation, housing status, body mass index (BMI), smoking history, and heavy alcohol use history.

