**10.2 Baseline (Visit B, one week before Visit 1.1)**

1. Urine drug test
2. Behavioral survey
3. Blood draws (~50 mL total) for:
  - a. PBMCs for transcriptome profiling (~34 mL)
  - b. HIV viral load (~6 mL)
  - c. COVID-19 immunoassay (~8.5 mL)
4. HIV medications review
5. Measure weight and height
6. Record any adverse events

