**10.8 Early withdrawal appointment**

1. Record any adverse events
2. Record reason for withdrawal if initiated by participant
3. Discuss reason for withdrawal if initiated by investigator
4. Note that participant-initiated withdrawals do not have to occur in-person, and can occur over remote communication (e.g., phone or email)

**II. Those in the Non-substance-using Control group will only have 4 visits, which will have the same components listed below:**

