### 15.2 Demographic and Baseline Characteristics

Sociodemographic and behavioral covariates will include age, race, education level, sexual orientation, employment, income, body mass index (BMI) which is a known risk factor for inflammatory gene expression and a standard biological covariate in social genomics analysis (11, 98-100), smoking history, heavy alcohol use history.

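### BMI is named as a standard covariate in 15.2 but is absent from the 15.6 adjustment lists, and weight and height are specified only for the contingency management (CM) baseline, not for controls

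*Combined protocol and SAP*

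**What the plan says.** **Covariates.** Section 15.2 says the covariates will include BMI, which it calls "body mass index (BMI) which is a known risk factor for inflammatory gene expression and a standard biological covariate in social genomics analysis". Section 15.6 gives two explicit adjustment lists. For Aim 1: "All models in Aim 1 will adjust for age, race, education, employment, housing, and mRNA encoding markers of major leukocyte subsets". For the psychosocial model: "We will control for age, race, education, and mRNA markers of major leukocyte subsets". Neither contains BMI. The further confounders that 15.6 says will be assessed are COVID-19 infection, liver function and type of antiretroviral prescription, again without BMI. Section 15.3 says of the two arms that "we will estimate, graph, and compare trajectories of CTRA gene expression" and names no covariates.

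**Measurement.** The synopsis lists "body mass index (BMI), smoking history, and heavy alcohol use history" among the other evaluations. Section 5.4 repeats the item ("housing status, body mass index (BMI), smoking history, and heavy alcohol use history"). Neither restricts it to one arm. The only collection step is "Measure weight and height" in 10.2, which falls under the heading for the CM group. For controls, the text that introduces 10.9 says they "will only have 4 visits, which will have the same components listed below". The list that follows has a urine test, survey, blood draws, HIV medication review and adverse events, but no weight or height. The screening demographics in 9.1.2 do not name them either.

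**The concern.** Allocation is by substance-use status, not by randomization (8.1), and 4.1 gives the control group the job of supplying a reference CTRA level against which CTRA in men with methamphetamine use disorder is compared. CTRA includes inflammatory genes, and 15.2 itself links BMI to inflammatory gene expression. If the arms differ in BMI, an unadjusted difference in CTRA level mixes the two.

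The plan does not say whether 15.2 or 15.6 governs. A detailed SAP, promised in section 15, can settle that at any time before the final analysis. It cannot supply a control baseline measurement that was never taken, so the data-collection part has to be put right while controls are still being seen.

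**Working it through.** The plan states no figure on this point, so there is none to reproduce. The check has a textual part and an illustrative numerical part.

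**1. Text side by side**

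| Place | BMI, or weight and height? |
|---|---|
| Synopsis, 5.4 (whole study) | BMI listed |
| 15.2 covariates | BMI listed, called standard |
| 15.3 arm comparison | no covariates named |
| 15.6 Aim 1 list | absent |
| 15.6 psychosocial list | absent |
| 15.6 further confounders | absent |
| 10.2 CM baseline | measured |
| 10.9 control visits | absent |
| Table 3, Appendix 2 | no row for either arm |

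From the steps actually specified, a BMI-adjusted version of the 15.3 model could not be fitted across both arms.

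**2. Size for a difference in CTRA level**

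From the documents: 35 CM participants, 20 controls, four visits. Assumed, because the documents give nothing: arm difference in BMI d (SD units), within-arm BMI-CTRA correlation r, and within-person correlation of CTRA (ICC) of 0.3 to 0.7. CTRA is in SD units, tests are two-sided at 0.05, and there is no true arm difference.

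- Shift in the unadjusted arm difference = r × d. Middle case: 0.2 × 0.5 = 0.10. Extremes: 0.1 × 0.2 = 0.02 and 0.3 × 0.8 = 0.24.
- Single-visit standard error = sqrt(1/35 + 1/20) = 0.280.
- Standard error of the four-visit mean = 0.280 × sqrt((1 + 3 × ICC)/4) = 0.193, 0.222 and 0.247 for ICC 0.3, 0.5 and 0.7.
- Rejection rate from the noncentral t distribution with 53 df and noncentrality shift/SE:

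| Shift | One visit | Four-visit mean, ICC 0.3 / 0.5 / 0.7 |
|---|---|---|
| 0.02 | 5.1% | 5.1% / 5.1% / 5.1% |
| 0.10 | 6.4% | 8.0% / 7.3% / 6.8% |
| 0.24 | 13.4% | 23.0% / 18.6% / 15.9% |

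**3. Size for a difference in trajectory**

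Write CTRA for person i at visit j as r × BMI_i + u_i + e_ij. A person's slope is a weighted sum over visits whose weights add to zero, so r × BMI_i and u_i both drop out and only e_ij remains. BMI therefore cannot shift the arm difference in slopes, provided its effect is the same at every visit. Simulation of the most adverse case above (d = 0.8, r = 0.3, ICC 0.5, four equally spaced visits) gave a rejection rate of about 5%, so no inflation.

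**4. Precision cost of adding BMI**

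SE ratio, adjusted to unadjusted = sqrt((1 − r²)/(1 − R²)), where R² = q d²/(1 + q d²) and q = (35/55) × (20/55) = 0.231. Middle case: q d² = 0.058, R² = 0.055, ratio = sqrt(0.96/0.945) = 1.008. Over the assumed ranges it runs from 0.958 (d = 0.2, r = 0.3) to 1.066 (d = 0.8, r = 0.1), that is, −4% to +7%.

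**The case against.** **The planned tests concern change, not level.** Section 15.3 compares trajectories, 15.6 tests a time-by-urine-result interaction, and the primary objective in 3.1 is about changes. This stands, and it limits the consequence to the level comparison in 4.1. A reader might infer from the upper rows of the table that the main test rejects up to 23% of the time. The documents do not support that: the figure belongs to a four-visit mean difference that no section specifies, at the extreme of inputs that are all assumed.

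**Section 15.2 may be the general covariate set**, with 15.6 adding model-specific terms. That reading is possible, since nothing says BMI is excluded. But the 15.6 lists repeat age, race and education from 15.2 and still leave BMI out, so the text does not settle which governs.

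**The control omission may be a drafting slip.** Section 10.9 is one list for four visits. It shows the COVID-19 assay at all four, whereas 9.2.3 has it at two, so a baseline-only item could easily have dropped out. The screening survey, which Table 3 assigns to both arms, collects self-reported health data and might hold height and weight, though 10.1 does not name them. A reader might therefore infer that BMI data will be missing for 20 of 55 participants (36%). The documents show only that no step is written for them. Table 3 and Appendix 2 add no evidence either way, because they have no such row for the CM arm, where the step is required. What remains is that staff following 10.9 would not take the measurement, and self-reported values would not match the measured CM values in kind.

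**BMI may be a consequence of methamphetamine use**, so adjusting could remove part of the difference of interest. This stands, and is a reason to show both results.

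**Smoking and heavy alcohol history** are also in 15.2 and missing from 15.6. A reader might want them in the primary model as well. Because 6.3 excludes controls with recent use, adjustment could not separate recent use from arm, so their omission leads to no change in the primary model.

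**Conclusion.** The inconsistency is real and holds on the text alone. A covariate that the plan itself calls standard is in neither 15.6 list, is not named in 15.3, and has a collection step in only one arm of a non-randomized comparison.

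The effect is modest and confined to the arm difference in CTRA level. It is about 6-8% rejection instead of 5% at the middle assumptions, essentially nil at the smallest, and larger only at the extremes. The trajectory contrast is unaffected as long as the BMI effect is constant over the 12 weeks. The actual confounding cannot be computed, because the documents give neither the BMI difference between arms nor its association with CTRA. The case for acting rests on the fact that the control measurement is cheap now and cannot be recovered later.

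**What to change.** 1. Add weight and height to the control baseline visit in 10.9, and a matching row for both arms in Table 3 and Appendix 2, so that BMI is measured the same way in both arms.
2. Reconcile 15.2 with 15.6, state which list governs, and include baseline BMI in the CTRA models of 15.3 and 15.6. Report results with and without it, because BMI may be a consequence of methamphetamine use.

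Cost: one brief measurement in 20 controls, a table row, some analysis-plan wording and one more model parameter, with a change in standard error of about −4% to +7% under the assumed inputs. The downside is possible over-adjustment, which the paired reporting makes visible.
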